**APPENDIX C RESPONSE CRITERIA FOR MULTIPLE MYELOMA**

**Table D1 Summary of International Myeloma Working Group-Uniform Response Criteria (IMWG-URC)**

Response Subcategory a	Response Criteria
sCR b	
 
Negative immunofixation on the serum and urine and
 
Disappearance of any soft tissue plasmacytomas and
 
< 5% plasma cells in bone marrow and
 
Normal SFLC ratio and
 
Absence of clonal cells in bone marrowc
 

CR b	
 
Negative immunofixation on the serum and urine and
 
Disappearance of any soft tissue plasmacytomas and
 
< 5% plasma cells in bone marrow
 

VGPR b, d	
 
Serum and urine M-protein detectable by immunofixation but not on electrophoresis or
 
≥ 90% reduction in serum M-component with urine M-component < 100 mg per 24 hours                             
 
If the serum and urine M-protein are not measurable, a decrease of > 90% in the difference between the involved and uninvolved sFLC levels is required in place of the M-protein criteria
 
 
 

PR b, d	
 
≥ 50% reduction of serum M-protein and reduction in 24-hour urinary M-protein by ≥ 90% or to < 200 mg per 24 hours
 
If the serum and urine M-protein are not measurable, a decrease ≥ 50% in the difference between involved and uninvolved FLC levels is required in place of the M-protein criteria.
 
If present at baseline, a ≥ 50% reduction in the size of soft tissue plasmacytomas is also requiredd, e
 

Stable	
 
Not meeting criteria for CR, VGPR, PR, or PD
 

PD e	
Any one or more of the following increase of ≥ 25% from lowest response value in:
 
 
Serum M-component (absolute increase must be ≥ 0.5 g/dL) and/or
 
Urine M-component (absolute increase must be ≥ 200 mg per 24 hours) and/or
 
Only in patients without measurable serum and urine M-protein levels: the difference between involved and uninvolved FLC levels (absolute increase must be > 10 mg/dL)
 
Only in patients without measurable serum and urine M-protein levels and without measurable disease by FLC levels, bone marrow plasma cell percentage (absolute percentage must be ≥ 10%)
 
Bone marrow plasma cell percentages (absolute % must be ≥ 10%)
 
 
Definite development of new bone lesions or soft tissue plasmacytomas or definite increase in size of existing bone lesions or soft tissue plasmacytomasf, g, h
 
Development of hypercalcemia (corrected serum calcium > 11.5 mg/dL or 2.65 mmol/L) attributed solely to the plasma cell proliferative disorder

Footnotes are defined on [next page](#)

Approved

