## 6 SUBJECT SELECTION

### 6.1 INCLUSION CRITERIA

#### Disease Related

2. Multiple myeloma that is primary refractory, relapsed and refractory, or intolerant after at least 2 lines of standard therapy for multiple myeloma, including:
  - a.  $\geq 2$  consecutive cycles of both bortezomib and lenalidomide or thalidomide (alone or in combination)
  - b. In the dose-expansion portion of the study only: In addition to the above, treatment with adequate alkylator therapy, defined as:
    - i. High-dose melphalan or other alkylating agent as conditioning for autologous or allogeneic SCT, or
    - ii.  $\geq 6$  cycles of induction therapy, or
    - iii. Progressive disease after  $\geq 2$  cycles

Approved

3. Measurable disease as indicated by 1 or more of the following:
  - a. Serum M-protein  $\geq$  500 mg/dL
  - b. Urine M-protein  $\geq$  200 mg/24 h
  - c. Only for subjects without measurable M-protein by serum protein electrophoresis (SPEP) and urine protein electrophoresis (UPEP), involved free light chain (FLC) concentration  $\geq$  10 mg/dL provided serum free light chain (SFLC) ratio is abnormal
4. Disease progression on or within 60 days of completion of the last therapy, or intolerance to bortezomib if received as their last therapy
  - a. Patients who received bortezomib as their last therapy who were not refractory but developed bortezomib intolerance, as defined by the development of Grade 2 peripheral neuropathy with pain or  $\geq$  Grade 3 peripheral neuropathy after  $\geq$  2 consecutive cycles, are eligible
5. Prior carfilzomib is allowed if a subject was not removed from carfilzomib therapy due to toxicity, unless approved by the **Sponsor's** study medical monitor.

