Serum free light chain assay and kappa:lambda (K/ $\lambda$ ) ratio will be conducted according to the schedule outlined in the Schedule of Assessments, [Appendices A1, A2, B1, and B2](#). Only in subjects without measurable serum and urine M-protein levels (serum M-protein  $< 0.5$  g/dL or urine M-protein  $< 200$  mg/24 hours) at Baseline will SFCLC assays be used to determine eligibility and response. In subjects with measurable SPEP and/or UPEP, SFCLC may be used in conjunction with those assessments to determine response per disease response criteria but only SPEP and/or UPEP will be used to determine eligibility.

All response categories (CR, sCR, VGPR, PR, MR, PD) require 2 consecutive assessments made at any time before the institution of any new therapy. All subjects will be followed until disease progression (confirmed by 2 consecutive measurements that are also verified by the **Sponsor's** medical monitor prior to treatment discontinuation), unacceptable toxicity, or withdrawal of consent, whichever occurs first.

Disease progression will be determined and confirmed with the medical monitor by two consecutive assessments using the IMWG-URC ([Appendices A1, A2, B1, and B2](#)).

Approved

Serum M component increases of  $\geq 1.0$  g/dL are sufficient to define progression if the starting component is  $\geq 0.5$  g/dL according to these criteria. However, it is understood from these criteria that a single measurement is adequate in cases of clear increased bone marrow plasma cell percentage, development of new or worsened bone lesions from a skeletal survey, or development of new or worsened soft tissue plasmacytomas.

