**Table D1 Summary of International Myeloma Working Group-Uniform Response Criteria (IMWG-URC) (cont'd)**

Response Subcategory a	Response Criteria
-----------------------------------	-------------------

Sources: [Blade 1998](#); [Durie 2006](#); [Rajkumar 2011](#).

CR = complete response; sCR = stringent complete response; FLC = free light chain; PD = progressive disease; PR = partial response; SFLC = serum free light chain; VGPR = very good partial response.

- a Subjects with measurable disease in both serum (SPEP) and urine (UPEP) at study entry are required to meet response criteria in both UPEP and SPEP in order to qualify for a PR or better. Conversely, it should be noted that criteria for progressive disease only needs to be met, and confirmed, in one parameter.
- b All response categories (CR, sCR, VGPR, PR) require two consecutive assessments made at any time before the institution of any new therapy, as well as no known evidence of progressive or new bone lesions if radiographic studies were performed. Radiographic studies are not required to satisfy these response requirements. Bone marrow assessments are not required to be confirmed by repeat testing.
- c Presence/absence of clonal cells is based on the  $\kappa/\lambda$  ratio. An abnormal  $\kappa/\lambda$  ratio by immunohistochemistry and/or immunofluorescence requires a minimum of 100 plasma cells for analysis. An abnormal ratio reflecting presence of an abnormal clone is  $\kappa/\lambda$  of  $> 4:1$  or  $< 1:2$ .
- d Response criteria for all categories and subcategories of response except CR and VGPR are applicable only to patients that have “measurable” disease defined by at least one of SPEP  $\geq 1.0$  g/dL or UPEP  $\geq 200$  mg per 24 hours; except for assessment of sCR, CR, or VGPR, patients with measurable disease restricted to SPEP will need to be followed only by SPEP. Correspondingly, patients with measurable disease restricted to UPEP will need to be followed only by UPEP.
- e Determination of PD based on M-protein, hypercalcemia, or FLC while on study requires two consecutive assessments made at any time before classification of progressive disease and/or the institution of new therapy. Serum M-component increases of  $\geq 1$  g/dL are sufficient to define progression if starting M-component is  $\geq 5$  g/dL.

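### The CR row of Table D1 has no free-light-chain condition, so a subject enrolled on light chains alone can be scored CR, and counted in ORR and CBR, without a qualifying light-chain fall

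*Protocol*

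**What the plan says.** Protocol Section 6.1, criterion 3c, opens a light-chain route to entry: "Only for subjects without measurable M-protein by serum protein electrophoresis (SPEP) and urine protein electrophoresis (UPEP), involved free light chain (FLC) concentration" must be at least 10 mg/dL, with an abnormal ratio. Section 11.3 then says that only in subjects without measurable serum and urine M-protein "at Baseline will SFCLC assays be used to determine eligibility and response".

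Appendix C gives the response rules. In Table D1, the PR row for subjects without measurable M-protein says that a fall of at least 50% "in the difference between involved and uninvolved FLC levels is required in place of the M-protein criteria". The VGPR row has the parallel rule with a fall above 90%, "in the difference between the involved and uninvolved sFLC levels is required in place of the M-protein criteria". The sCR row lists "Normal SFLC ratio" among its items, and the PD row has a light-chain rise rule. The CR row starts with "Negative immunofixation on the serum and urine" and adds only disappearance of soft-tissue plasmacytomas and marrow plasma cells below 5%.

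Footnote d to Table D1 begins: "Response criteria for all categories and subcategories of response except CR and VGPR are applicable only to patients" with disease measurable by SPEP or UPEP. CR and VGPR are therefore outside that restriction.

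CR counts as a response in ORR (Protocol 14.5.2, SAP 7.5.1) and, as PR or better, in CBR (Protocol 14.5.2). The SAP refers to the IMWG-URC and adds no light-chain rule of its own.

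**The concern.** For a subject enrolled on FLC alone, the involved light chain is the marker that made the disease measurable. Every graded response from MR upward, and progression, is tied to it, except CR. A subject whose light chains have not moved enough for PR can therefore satisfy every item of a category that ranks above PR.

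If that happens, a non-response in the defining marker is recorded as a response. It enters ORR and CBR, and it also enters the duration-of-response analysis, because SAP 7.5.2 includes subjects with CR. Response is assessed by the investigator in an open-label study, and the SAP has no rule that would catch the case.

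**Working it through.** **Light-chain condition by category, for subjects without measurable serum and urine M-protein.** Let D be the baseline involved-minus-uninvolved difference, d the current one and L the lowest one so far.

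- sCR (Table D1): normal ratio required.
- CR (Table D1): none.
- VGPR (Table D1): fall above 90%, so d < 0.10 D.
- PR (Table D1): fall of at least 50%, so d ≤ 0.50 D.
- MR (Table D2): fall of 25% to 49%.
- PD (Table D1): d ≥ 1.25 L and d − L > 10 mg/dL.

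For any d above 0.50 D that does not meet the PD rule, the subject fails PR and VGPR on light chains, while the CR row stays open. A subject in that band whose fall is 25% to 49% would be MR and already in CBR, so CR changes only ORR. A smaller fall, no change or a sub-PD rise would be stable disease, so CR changes both rates.

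**Do the footnotes close it?** Footnote a concerns subjects measurable in both serum and urine. Footnote b requires two consecutive assessments and no known progressive or new bone lesions, and exempts marrow from repeat testing. Footnote d exempts CR from the measurability restriction. None adds a light-chain condition to CR.

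**Can the CR items be met without a light-chain response?** Section 6.1 requires neither positive immunofixation nor a minimum marrow plasma-cell percentage at entry. Section 11.3 calls for on-study serum immunofixation when the previous SPEP is undetectable. A subject who enters with undetectable SPEP could thus be negative from the start.

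**The plan's own figure.** Protocol 14.7 gives about 94% for at least 7 responses in 26 subjects at a true ORR of 40%. The exact binomial gives P(X ≥ 7 | n = 26, p = 0.40) = 0.944, which agrees. The point here does not alter that figure.

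**Effect of one misscored subject.** 1/26 = 3.8 points. With exact 95% intervals, 6/26 = 23.1% (9.0 to 43.6) becomes 7/26 = 26.9% (11.6 to 47.8).

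**Illustration under assumptions.** Neither input is in the documents. Let f be the share of FLC-only subjects, q the share of their non-responders scored CR, and p the true ORR.

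- Apparent ORR = p + f(1 − p)q.
- With p = 0.30, f = 0.10, q = 0.25: 0.30 + 0.10 × 0.70 × 0.25 = 0.3175. P(at least 7 of 26) goes from 0.703 to 0.766. The expected number misscored is 26 × 0.0175 = 0.46.
- Over f = 5% to 20% and q = 5% to 100%: apparent ORR 30.2% to 44.0%, P(at least 7) 0.710 to 0.977. The upper end is a bound, not an expectation.

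**The case against.** The strongest reply is that the path is narrow. CR still needs negative serum and urine immunofixation, no plasmacytoma, a marrow below 5%, confirmation and no progression. Not measurable does not mean absent: a subject with a small M-protein can be immunofixation-positive and would need real clearance. On-treatment marrow is taken only when clinically indicated to confirm CR, so the investigator must already suspect CR while light chains are flat. Section 11.3 shows the intent to use FLC for response, and Table D1 calls itself a summary, so the full cited criteria might supply a rule. That cannot be checked from these documents. ORR is secondary and descriptive.

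All of this limits frequency and importance, but none of it supplies a CR threshold. Section 11.3 states a principle that the CR row does not carry out.

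Four stronger readings are tempting and not supported:

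- A reader might infer that CR is easier than PR for these subjects. It has other and demanding conditions; what it lacks is the light-chain one.
- A reader might infer that one low marrow sample is enough. Footnote b exempts only the marrow from repetition, and the other CR conditions remain.
- A reader might take an assumed 10% to 20% of 26, or 2.6 to 5.2 subjects, as the number of false CRs. That would count FLC-only enrolment, not misscored subjects.
- A reader might infer from the 'or' in the Section 11.3 parenthesis that subjects measurable in serum only are drawn into the FLC group. The words before the parenthesis say serum and urine, and the next sentence treats subjects with measurable SPEP or UPEP separately. It is an editorial slip.

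**Conclusion.** The gap is real on the text. Subjects may enter on FLC alone, FLC is said to determine their response, all the neighbouring categories use it, and CR does not. Such a subject can be scored CR and counted in ORR and CBR with light chains flat, falling by less than 50%, or rising by less than the PD rule.

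The size is 3.8 points of ORR per misscored subject at n = 26. The total cannot be fixed, because the documents give neither the number of FLC-only subjects nor how many could meet the remaining CR items without a light-chain response. The DLT and MTD conclusions do not use response and are unaffected.

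Footnote d adds a related inconsistency. Read literally, it limits PR to subjects measurable by SPEP or UPEP, which contradicts the FLC rule in the PR row.

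**What to change.** 1. Add to the CR row of Table D1: *if serum and urine M-protein are not measurable at baseline, a normal SFLC ratio is also required.* The table already uses this condition for sCR.
2. Put the same sentence in SAP 7.5.1 and apply it to CBR. The SAP governs the abbreviated report, and the protocol's opening note says Amendment 3 was not implemented, so the SAP is the practical place. It should be settled before database lock.
3. Reconcile footnote d with the PR row so that PR by FLC is clearly available to these subjects. This belongs with item 1: a subject with a genuine light-chain fall but a ratio still abnormal should move from CR to VGPR or PR and remain a responder. Footnote d read literally would leave no PR category for that subject.
4. Optionally, change 'or' to 'and' in the Section 11.3 parenthesis, as an editorial correction.

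The cost is one line in the table, one sentence in the SAP and a footnote edit. SFLC is already among the disease assessments in Section 11.3, so no new data are needed. Listing FLC-only subjects with a best response of CR would show how many are affected.

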## 11.2 LABORATORY EVALUATIONS FOR SAFETY

Laboratory tests, including hematology, blood chemistries, and coagulation tests during scheduled visits, will be performed locally. Unscheduled or additional laboratory samples may be collected and analyzed by local laboratories if results are necessary for management of treatment-emergent AEs or dose modification.

Approved

The schedule for laboratory evaluations for safety is outlined in [Appendices A1, A2, B1,](#) and [B2](#). The laboratory tests included in the full chemistry panel are defined in [Table 16](#).

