## **11.3 DISEASE RESPONSE ASSESSMENTS**

The schedule of disease assessments for treated subjects is provided in [Appendices A1, A2, B1, and B2](#). Disease response will be assessed by the investigator. Beginning with Cycle 1, assessments are to be completed at the end of every 4-week cycle for the first 18 months of study treatment, and then at the end of every other cycle (every 8 weeks), beginning with Month 20, for the remainder of study treatment. Response assessment will be according to the IMWG-URC and modified EBMT guidelines ([Appendix C](#)). Disease response and progression assessments include:

- Serum protein electrophoresis (SPEP)
- Urine protein electrophoresis (UPEP)
- Serum immunofixation, serum free light chain (SFLC)
- Urine immunofixation
- Serum calcium
- Bone marrow sample as clinically indicated to confirm CR
- Radiographic assessments including plasmacytoma evaluation if baseline assessments were positive and as clinically indicated per the response criteria

Approved

CONFIDENTIAL

- Skeletal survey if baseline assessments were positive and as clinically indicated per the response criteria

Serum protein electrophoresis and immunofixation assessments will be conducted according to the schedule outlined in [Appendices A1, A2, B1, and B2](#), Schedule of Assessments.

Immunofixation will only be required after Screening, Baseline (Day -7 to 1), and End of Study Treatment, if results of the previous SPEP are zero/undetectable.

Urine protein electrophoresis and immunofixation will be performed on a 24-hour urine specimen collected from all subjects during the Screening period, Baseline (Day -7 to 1), and at the End of Study Treatment visit. The UPEP with 24-hour urine collection will be conducted according to the schedule outlined in [Appendices A1, A2, B1, and B2](#), Schedule of Assessments, and is required: 1) only if Baseline UPEP was  $\geq 200$  mg/24 hours, and 2) to confirm a disease response or disease progression. If the Baseline UPEP was negative, spot urine is required at each time point. If positive for paraprotein, a 24-hour urine collection with UPEP must be done at the next assessment and at each subsequent assessment unless the UPEP shows an absence of paraprotein.

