7.5 Efficacy Analyses

All efficacy analyses will be based on the Safety Population. Disease progression as collected at the end of treatment (end of study visit) as determined by the investigator will be used for the analysis for DOR.

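### The hypercalcemia criterion for progressive disease pairs two calcium cut-offs, 11.5 mg/dL and 2.65 mmol/L, that are not equivalent, and neither document says which one governs

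*Protocol*

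**What the plan says.** Table D1 in Appendix C of the protocol summarises the IMWG response criteria. Its PD row includes new hypercalcemia, defined as a corrected serum calcium above "11.5 mg/dL or 2.65 mmol/L) attributed solely to the plasma cell proliferative disorder". No other calcium threshold for progression appears in either document, and no text says that the two figures are meant to differ or which takes precedence.

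The surrounding rules are these:

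- One criterion is enough. Footnote a to Table D1 says that "criteria for progressive disease only needs to be met, and confirmed, in one parameter".
- It must be confirmed. Footnote e says: "Determination of PD based on M-protein, hypercalcemia, or FLC while on study requires two consecutive assessments".
- "Serum calcium" is on the list of response and progression assessments in Protocol Section 11.3, which also says: "Disease response will be assessed by the investigator".
- Protocol Section 11.2 says: "Laboratory tests, including hematology, blood chemistries, and coagulation tests during scheduled visits, will be performed locally". No reporting unit is prescribed.
- Protocol Sections 11.3 and 12.1 require the sponsor's medical monitor to verify progression before a subject stops study treatment.
- SAP Section 7.5 states that disease progression "as determined by the investigator will be used for the analysis for DOR".

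**The concern.** A threshold printed in two units should be one quantity. If the conversion is wrong, the table holds two thresholds, and a patient whose calcium falls between them has no defined status. Here the criterion is decisive: hypercalcemia alone, once confirmed and attributed to the myeloma, is PD. Under Protocol Section 10.1, PD ends oprozomib treatment. PD is also an event for DOR (SAP Section 7.5.2) and for the PFS listing (Protocol Section 14.5.2). Calcium is measured locally, with about 35 sites planned (Protocol Section 5), so the choice of value could follow the unit on the laboratory report rather than the disease.

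**Working it through.** **Inputs.** The two cut-offs, 11.5 mg/dL and 2.65 mmol/L, are from Table D1. The molar mass of calcium is not in the documents. I take 40.078 g/mol and check 40.0 to 40.1.

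**Formula.** mmol/L = (mg/dL × 10) / molar mass; mg/dL = (mmol/L × molar mass) / 10.

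**Does the printed pair reproduce?**

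- 11.5 × 10 / 40.078 = 2.869, so 11.5 mg/dL is 2.87 mmol/L, not 2.65.
- 2.65 × 40.078 / 10 = 10.621, so 2.65 mmol/L is 10.62 mg/dL, not 11.5.
- Gap: 11.5 − 10.621 = 0.879 mg/dL, or 2.869 − 2.65 = 0.219 mmol/L. That is 0.879 / 11.5 = 7.6% of the higher cut-off.

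| Molar mass (g/mol) | 11.5 mg/dL in mmol/L | 2.65 mmol/L in mg/dL | Gap (mg/dL) |
|---|---|---|---|
| 40.0 | 2.875 | 10.60 | 0.90 |
| 40.078 | 2.869 | 10.62 | 0.88 |
| 40.1 | 2.868 | 10.63 | 0.87 |

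**Can the mismatch be explained away?**

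- Rounding: anything that rounds to 11.5 mg/dL (11.45 to 11.55) is 2.857 to 2.882 mmol/L. Anything that rounds to 2.65 mmol/L (2.645 to 2.655) is 10.60 to 10.64 mg/dL. The intervals do not meet.
- A unit mislabel: in mEq/L, 11.5 mg/dL is 2.869 × 2 = 5.74, which is not 2.65 either.
- The molar mass that would make the pair agree is 11.5 × 10 / 2.65 = 43.4 g/mol, well outside the range for calcium.

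**What falls in the gap.** A corrected calcium above 10.62 and up to 11.5 mg/dL (above 2.65 and up to 2.87 mmol/L) exceeds the SI figure but not the conventional one. For example, 11.0 mg/dL is 11.0 × 10 / 40.078 = 2.74 mmol/L.

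**What the text then means.** There are two readings:

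1. The *or* gives one cut-off in two units. The conversion is then wrong, and the threshold in force depends on which figure the reader uses.
2. The *or* means that either figure qualifies. The lower one (10.62 mg/dL) then applies everywhere and 11.5 mg/dL has no function.

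The table is defective on both readings, but only the first can produce differences between sites.

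**The case against.** The arithmetic is hard to dispute; the case on the other side is about consequence.

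- **Site differences are not shown.** A reader might infer that the same calcium is in fact progression at SI-unit sites and not at conventional-unit sites. The documents do not support that: no site is identified as reporting in SI units. The protocol's other concentration limits, such as M-protein, free light chain, creatinine and glucose, are mostly in conventional units. On the either-value reading no site difference arises. This stands, and the between-site effect can only be stated conditionally.
- **There are safeguards.** The rise must be attributed solely to the plasma cell disorder and seen on two consecutive assessments, and one sponsor-side function verifies PD before treatment stops. These narrow the affected group, and central verification should limit inconsistency between sites. But a stable value in the gap is confirmed on repeat, and the monitor has the same two figures and no rule for choosing between them.
- **The endpoints are minor.** DLTs and safety are primary; response, clinical benefit and PK are secondary. DOR and PFS are in neither list: DOR has a descriptive Kaplan–Meier summary, and PFS is only listed. This stands and bounds the importance of the point.
- **The pair may have been copied.** Table D1 is a summary of cited criteria that are not available here, so its origin was not checked. Copying would not make the values equal, but a correction might then be a departure from the cited standard that needs recording.
- **It is late to act.** Amendment 3 (Protocol Section 3.1 and Appendix Q) records the analysis and the abbreviated report as complete, so a check before database lock may no longer be possible. This affects the form of the remedy, not the defect.

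**Conclusion.** Table D1 is wrong as written. It gives a decision threshold as two values 0.88 mg/dL apart (0.87 to 0.90 over the molar masses checked), and nothing in the protocol or SAP settles which applies.

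The size of the effect on results is unknown. It is zero if everyone used one figure, or if no subject's PD rested on calcium in the gap. At most it reaches every subject whose PD was triggered only, or first, by a confirmed calcium above 10.62 and up to 11.5 mg/dL attributed solely to myeloma. The documents give no count. Systematic misclassification by laboratory unit is a possibility that depends on site practice, not a finding.

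Where there is an effect, it falls on the timing of PD, PD-driven discontinuation, the DOR summary and the PFS listing. ORR could be touched only indirectly, and the DLT/MTD endpoints and the sample size not at all.

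The conclusion rests on the molar mass of calcium. It also assumes that Amendment 2, under which the study ran, printed the same pair; Amendment 3's summary of changes lists no revision to the response-criteria table.

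**What to change.** 1. Reconcile the two values in Table D1. State one governing threshold and give its correct conversion: 11.5 mg/dL pairs with 2.87 mmol/L, and 2.65 mmol/L pairs with 10.62 mg/dL. Which threshold should govern is for the sponsor and its clinical advisers; this review does not say. Record any departure from the cited criteria.
2. State the formula for corrected calcium. Neither document gives one, and the check below cannot be reproduced without it.
3. List every PD determination that rested on hypercalcemia alone, or for which hypercalcemia was the first trigger, and compare it with the governing threshold. If the lower value governs, also look for subjects with two consecutive values in the gap who were not called PD; their attribution would need clinical judgement.
4. Report any reclassification, and its effect on DOR and PFS, in the study report or an addendum. SAP Section 1 already provides for documenting changes to planned analyses in the abbreviated report.

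The cost is one corrected figure, one stated formula and a short listing review. Calcium and albumin are both in the full chemistry panel (Protocol Table 16), so no new data should be needed.
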